3.1 Measures Taken to Minimize Bias

Once all results determining the eligibility of the subject are available and reviewed by the Medical Monitor/Expert (MM), the subject will be centrally allocated to 1 of 2 cohorts: either TransCon hGH or Genotropin, in a 2:1 ratio, and allocated to strata using the minimization rule according to their age (≤ 6 and > 6 years), peak growth hormone (GH) levels in stimulation tests (≤ 5 ng/mL and > 5 ng/mL), and gender. For the stratum peak GH levels in stimulation tests (≤ 5 ng/mL and > 5 ng/mL), the stratum will be allocated based on the highest GH value of the 2 stimulation tests. The subject will be assigned a unique randomization number along with the cohort allocation. The trial auxologists will be trained and kept blinded to treatment allocation as far as possible at each site.

All efforts will be made to keep missing data to a minimum, including the following:

1. Investigators will be trained about the importance of retention
2. Investigators will be instructed to encourage complete follow-up for all subjects, including any subjects who might discontinue either weekly TransCon hGH or daily Genotropin therapy
3. The Informed Consent Form (ICF) and Assent Form will include a statement educating subjects and parents/legal guardians about the scientific importance of their data even if the subject discontinues study treatment early
4. Special efforts will be made to provide assistance to subjects/families who might discontinue due to travel or cost barriers, such as offers of transportation to the clinic
5. Most visits have visit windows to allow flexibility of clinic attendance (see Sections 10.1.2.1 and 10.1.2.2 of protocol)
6. Every effort will be made to contact subjects/legal guardians or other family members in order to maintain contact with the clinic

This is an open-label trial. Due to different dose frequencies and dosing techniques, it is not deemed suitable to employ blinding methods between TransCon hGH and Genotropin treatment assignment. However, attempts will be made to keep the the Sponsor staff (especially the MM) blinded to treatment. Any necessary unblinding to the Sponsor staff for safety purposes will be documented before database lock.

Subjects will be identified by a Subject Number (allocated at Screening), consisting of 3 digits to indicate the site and 2 digits specific for the subject.

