8.1 Primary Efficacy Variable Analysis

The absolute values and mean change from baseline at each timepoint of the annualized height velocity will be presented by treatment group with descriptive statistics.

The primary endpoint, annualized height velocity at week 52, will be compared between TransCon hGH treatment and daily hGH treatment, by a non-inferiority comparison with a non-inferiority margin of 2.0 cm/year, followed by a test of superiority if non-inferiority is established.

As the primary analysis, an ANCOVA model will be used to analyze annualized height velocity at week 52, after potential multiple imputation as described in [Section 6.1.2](#). The annualized height velocity at week 52 will be included in the model as a response variable. The model will include baseline age, peak GH levels (log transformed) at stimulation test, baseline height SDS – average SDS of parental height as covariates, treatment and gender as factors. The estimates from the 100 fitted models for each of the 100 imputed datasets will be combined to provide an overall estimate of the between treatment group difference with a corresponding confidence interval and a p-value.

For the primary efficacy analysis, a 2-sided 95% confidence interval will be calculated for the difference in least square means between the 2 treatment groups [TransCon hGH treatment minus daily hGH] at Week 52. If the lower confidence bound is >-2.0 cm, non-inferiority is demonstrated in terms of effectiveness. If the lower confidence bound is >0 , superiority is established.

Treatment-by-covariate interaction will be examined as appropriate as part of the analysis model examination.

Height velocity at other post-baseline visits will be analyzed similarly using the same ANCOVA model as described above for the primary efficacy analysis. The same ANCOVA model described above will also be used to analyze observed cases as a sensitivity analysis of the primary analysis.

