8.2 Secondary Efficacy Variable Analysis

The absolute values and mean change from baseline at each timepoint of other secondary efficacy endpoints will be presented by treatment group with descriptive statistics. Height velocity SDS will also be summarized. Mixed model for repeated measurement (MMRM) models will be used for the following continuous secondary efficacy endpoints. Missing data will not be imputed before conducting the MMRM model. The MMRM model for height velocity will include baseline age, peak GH levels (log transformed) at stimulation test, baseline height SDS – average SDS of parental height, as covariates, gender as a fixed factor, and subject as a random effect. The MMRM model for all the following continuous variables will include treatment, timepoint, and treatment by timepoint interaction.

- height velocity
- change in height SDS
- serum IGF-1 levels
- serum IGFBP-3 levels
- IGF-1 SDS
- IGFBP-3 SDS

The MMRM model for change in height SDS, IGF-1, IGFBP-3, IGF-1 SDS and IGFBP-3 SDS will include baseline age, peak GH (log transformed), baseline (of the corresponding variable) as covariates, and gender as a factor.

For the patients who are in PK/PD population, the average values from hour 48 and hour 72 at Visit 3 (Week 13) will be considered as the Visit 3 value for IGF-1, IGF-1 SDS, IGFBP-3 and IGFBP-3 SDS, and used in the analyses for Visit 3.

Two sided 95% confidence intervals will be calculated for the difference in least square means between the 2 treatment groups. Change from baseline will be summarized when appropriate as supportive analyses.

The rate of subjects achieving normalization of serum IGF-1 SDS will be calculated by treatment group and visit defined as SDS scores of 0 to 2.0. Additionally, cut points of -2.0 to +2.0 and -1.0 to +2.0 will be assessed. The following IGF-1 SDS variables will be derived:

- Average IGF-1 SDS at visits 3, 4, and 5
- Proportion of subjects achieving normalization of IGF-1 SDS of 0 to 2.0 based on the average IGF-1 SDS at visits 3, 4, and 5

The rates of subjects achieving IGF-1 SDS 0-2.0 will be analyzed by logistic regression adjusting for baseline age and baseline IGF-1 SDS. In case of model convergence issues caused by sparse cells, Fisher's exact test will be carried out instead.

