8.3 Average IGF-1 SDS at Week 52 based on population PK/PD modeling

Due to differences in the PD profiles of the two treatment groups, the analysis of superiority in IGF-1 SDS described in [Section 8.2](#) will be supported by the analysis of average IGF-1 SDS starting from Visit 3 (Week 13) to end of study. The average IGF-1 SDS at Week 52 group will be calculated based on the following steps:

1. A non-linear mixed model by treatment will be conducted for IGF-1 concentration data, based on rich sampling data from the Phase 2 study in growth hormone deficient pediatrics (Ascendis Pharma study no. ACP-001 CT-004), and from the rich sampling in the PK/PD population in this study, and from all sampling data at steady state (visits 3-6) from the rest of the subjects in this study.
2. The non-linear mixed model of IGF-1 concentration will be fitted to describe relationship of dose, time since dosing to IGF-1 concentration. The most simple compartment model which can sufficiently explain IGF-1 kinetics will be selected and goodness of fit will be assessed based on standard model diagnostics.
3. The weekly IGF-1 AUC (0-168 hours after dosing) will be calculated for each individual subject based on the non-linear mixed model established from Step 2.
4. The weekly average IGF-1 concentration for each subject is calculated as:
$$\text{Weekly average IGF-1 concentration} = \text{Weekly IGF-1 AUC (from Step 3)} / 168.$$
5. The average IGF-1 SDS at Week 52 is determined based on the weekly average IGF-1 concentration in Step 4 for each individual subject.

The average IGF-1 SDS at Week 52 will be analyzed by an analysis of covariance (ANCOVA) model with the same model covariate selection as described for the MMRM model in [Section 8.2](#). The proportion of subjects achieving average IGF-1 SDS within 0-2.0 will be analyzed with the same logistic regression model as described in [Section 8.2](#).

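### The logistic model for IGF-1 normalisation omits gender and peak GH, two of the three minimisation factors, while the companion IGF-1 SDS models include both and no reason is given

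*SAP*

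**What the plan says.** **Allocation.** SAP 3.1 has subjects "allocated to strata using the minimization rule according to their age" (cut at 6 years), peak stimulated GH (cut at 5 ng/mL) and gender. Protocol 7.1.2 gives the same three factors.

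**Binary IGF-1 analysis (SAP 8.2).** "The rates of subjects achieving IGF-1 SDS 0-2.0 will be analyzed by logistic regression adjusting for baseline age and baseline IGF-1 SDS". The fallback is unadjusted: "In case of model convergence issues caused by sparse cells, Fisher's exact test will be carried out instead".

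**Continuous IGF-1 analyses (SAP 8.2).** The MMRM for change in height SDS, IGF-1, IGFBP-3 and their SDS versions "will include baseline age, peak GH (log transformed), baseline (of the corresponding variable) as covariates, and gender as a factor", together with treatment, timepoint and their interaction.

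**Modelled average IGF-1 SDS (SAP 8.3).** The ANCOVA takes its covariates from the MMRM in 8.2. The proportion within 0 to 2.0 "will be analyzed with the same logistic regression model as described in" 8.2.

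**Primary analysis (SAP 8.1).** "The model will include baseline age, peak GH levels (log transformed) at stimulation test", along with gender and the difference between baseline height SDS and parental height SDS.

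Protocol 13.4.4 announces a test of proportions for this endpoint but names no covariates, so nothing there supplies the two missing factors.

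**The concern.** An analysis should normally adjust for the factors that allocation balanced on. If those factors predict the outcome and are left out, the model-based test does not use the balance that the design created and tends to be conservative. In a logistic model the treatment odds ratio also moves towards 1, even with perfect balance.

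There is a coherence problem as well. The continuous and binary versions of IGF-1 SDS rest on different covariate sets within one section, and again in 8.3. If the two disagree, a reader cannot tell whether dichotomising or the change of covariates is responsible. By putting gender and peak GH in the IGF-1 SDS MMRM, the SAP already treats them as relevant to this variable.

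At stake is how a named secondary endpoint, tested at a nominal two-sided 0.05, is estimated and interpreted. The trial's main claim is not at stake.

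**Working it through.** **1. Covariates side by side**

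| Analysis | Age | Peak GH | Gender | Baseline of the variable |
|---|---|---|---|---|
| Minimisation (SAP 3.1) | yes | yes | yes | – |
| Primary ANCOVA (8.1) | yes | yes (log) | yes | no (height SDS minus parental SDS instead) |
| IGF-1 SDS MMRM (8.2) | yes | yes (log) | yes | yes |
| IGF-1 SDS ANCOVA (8.3) | yes | yes (log) | yes | yes |
| Logistic, SDS 0 to 2.0 (8.2 and 8.3) | yes | **no** | **no** | yes |
| Fisher fallback (8.2) | no | no | no | no |

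**2. The plan's own figure.** The only sample size stated is for height velocity (SAP 3.2: SD 3.5 cm/year, margin 2.0 cm, one-sided alpha 0.025, power 90%, 2:1). The control-arm number is

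n = (z₀.₉₇₅ + z₀.₉₀)² × SD² × (1 + 1/2) / margin² = (1.960 + 1.282)² × 12.25 × 1.5 / 4 = 48.3, rounded up to 49.

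That gives 49 + 98 = 147, which matches the SAP. This figure does not depend on the logistic model, and no power is stated for IGF-1 normalisation.

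**3. Size of the effect, by simulation.** The documents give no prognostic effects and no normalisation rates, so the following are assumptions:
- 150 subjects, 2:1 minimisation on the three factors, with a 0.8 chance of the preferred arm.
- Age uniform from 3 to 12.5 years, 75% boys, log peak GH normal around log 5 with SD 0.7 and capped at log 10.
- Baseline IGF-1 SDS at or below about −1 and mildly related to peak GH.
- About 50% normalised in the control arm at reference covariate values; log-odds slopes of 0.1 per year of age and 0.5 per unit of baseline SDS.
- The same odds ratio for gender and per log unit of peak GH.

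There were 3,000 runs per row. Each cell shows the SAP model, then the model with gender and log peak GH added.

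| Prognostic OR | Power at treatment OR 2.5 | Median treatment OR | Rejection rate at treatment OR 1 |
|---|---|---|---|
| 1 | 72.1% / 72.3% | 2.58 / 2.61 | 5.4% / 5.5% |
| 1.5 | 69.4% / 70.1% | 2.50 / 2.59 | 3.9% / 4.1% |
| 2 | 64.9% / 67.6% | 2.42 / 2.57 | 4.8% / 5.1% |
| 3 | 60.2% / 64.4% | 2.29 / 2.59 | 4.1% / 5.4% |

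The Monte Carlo standard error of the last column is √(0.05 × 0.95 / 3000), or 0.4 points. The power loss runs from 0.2 to about 4 points.

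**4. Where the gain comes from.** Adjustment does not shrink the standard error of the log odds ratio. In the bottom row the mean standard error rises from 0.383 to 0.417, but the log odds ratio rises more. The ratio of estimate to standard error goes from ln 2.29 / 0.383 = 0.829 / 0.383 = 2.16 to ln 2.59 / 0.417 = 0.952 / 0.417 = 2.28. In the top row it is 2.53 for both models, so adding the terms costs almost nothing when they do not matter.

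**5. How large the prognostic odds ratios could be.** The outcome is a window, so P = Φ((2 − μ)/σ) − Φ(−μ/σ). Take two covariate groups whose mean SDS differs by 0.5, with σ assumed to be 1.0 to 1.3:
- Group means centred on 0, σ = 1.0: P = 0.389 and 0.559, odds ratio 1.99.
- Centred on 0.5, σ = 1.3: P = 0.487 and 0.550, odds ratio 1.29.
- Centred on 1.0: P is equal in the two groups, odds ratio 1.0.

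An odds ratio near 4 needs a shift of about 1.0 SDS in the most favourable of these cases (centred on 0, σ = 1.0: 0.302 and 0.625, odds ratio 3.84).

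**The case against.** **The endpoint is not confirmatory.** This stands. SAP 8.6 controls familywise error over non-inferiority and then superiority in height velocity only, and the document history records that IGF-1 was taken out of hypothesis testing. A reader might infer from Protocol 13.4, which lists the IGF-1 proportion as a third sequential test, that a confirmatory claim depends on this model. It does not, because Protocol 13 makes the final SAP the analysis of record.

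**The error is on the safe side.** This also stands. The simulation shows no inflation of type I error, so the omission is not a route to a false superiority finding.

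**Odds ratios are non-collapsible.** This stands in part. With fewer covariates the model targets a different conditional odds ratio, and both are valid under randomisation. The shift towards 1 is therefore not all bias, but the power loss remains.

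**IGF-1 SDS is already standardised for age and sex (SAP 11.1.3).** This weakens the case for gender but does not answer the point. Age is standardised too and is kept in the logistic model, gender is kept in the IGF-1 SDS MMRM, and peak GH is not standardised at all.

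**A short list suits a binary outcome in about 150 subjects.** This could be a good reason, but the SAP does not give it. Sparse cells appear only as the trigger for Fisher's test. Peak GH is also set to 2 ng/mL by convention where stimulation data are missing (SAP 6.1.2), yet that does not keep it out of the other models.

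**The adjusted picture is available elsewhere.** This is partly true. The MMRM and the 8.3 ANCOVA adjust for both factors, and 8.5 summarises efficacy by gender and GH stratum. None of these gives an adjusted analysis of the proportion.

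**A larger loss.** A reader might infer a loss of about 7 points. A simulation with stratified 2:1 allocation gave 58.3% against 65.1% when the odds ratios for gender and peak-GH stratum were set to 3 and 4. A run at the same odds ratios with baseline IGF-1 SDS in both models gave 56.6% against 62.0%, about 5 points. The documents support no effects of that size, and step 5 of the working suggests they would be hard to reach.

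**Fisher's test.** A reader might also infer that the fallback is invalid. It is a prespecified, valid test; preferring a penalised fit is a matter of choice.

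**Conclusion.** The inconsistency is real and is established by the text alone: the logistic model in 8.2 and 8.3 omits two of the three minimisation factors, the companion IGF-1 SDS models include them, and no reason is given. It is a modest specification fault in a secondary analysis. The consequence is a somewhat conservative test and a treatment odds ratio nearer 1. The power loss is about 0 to 4 points for prognostic odds ratios of 1 to 3, with no type I inflation. Those sizes rest on the assumed treatment odds ratio of 2.5, control rate and covariate distributions. The finding that factors are missing does not rest on them. The primary conclusion, the familywise error and the sample size of 147 are unaffected.

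**What to change.** In SAP 8.2, add gender as a factor and log-transformed peak GH as a covariate to the logistic model, so that its list matches the IGF-1 SDS MMRM. Section 8.3 refers back to that model and needs no separate edit.

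The cost is one sentence of SAP wording and two model terms, with no new data because both variables are already collected. The downside is slightly more risk of non-convergence when cells are sparse. Optionally, name a penalised (Firth) fit of the same model as the first fallback, with Fisher's exact test after it.

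If the sponsor prefers the shorter list, the SAP should state why and prespecify the full model as a sensitivity analysis.

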8.3 Average IGF-1 SDS at Week 52 based on population PK/PD modeling

Due to differences in the PD profiles of the two treatment groups, the analysis of superiority in IGF-1 SDS described in [Section 8.2](#) will be supported by the analysis of average IGF-1 SDS starting from Visit 3 (Week 13) to end of study. The average IGF-1 SDS at Week 52 group will be calculated based on the following steps:

1. A non-linear mixed model by treatment will be conducted for IGF-1 concentration data, based on rich sampling data from the Phase 2 study in growth hormone deficient pediatrics (Ascendis Pharma study no. ACP-001 CT-004), and from the rich sampling in the PK/PD population in this study, and from all sampling data at steady state (visits 3-6) from the rest of the subjects in this study.
2. The non-linear mixed model of IGF-1 concentration will be fitted to describe relationship of dose, time since dosing to IGF-1 concentration. The most simple compartment model which can sufficiently explain IGF-1 kinetics will be selected and goodness of fit will be assessed based on standard model diagnostics.
3. The weekly IGF-1 AUC (0-168 hours after dosing) will be calculated for each individual subject based on the non-linear mixed model established from Step 2.
4. The weekly average IGF-1 concentration for each subject is calculated as:
$$\text{Weekly average IGF-1 concentration} = \text{Weekly IGF-1 AUC (from Step 3)} / 168.$$
5. The average IGF-1 SDS at Week 52 is determined based on the weekly average IGF-1 concentration in Step 4 for each individual subject.

The average IGF-1 SDS at Week 52 will be analyzed by an analysis of covariance (ANCOVA) model with the same model covariate selection as described for the MMRM model in [Section 8.2](#). The proportion of subjects achieving average IGF-1 SDS within 0-2.0 will be analyzed with the same logistic regression model as described in [Section 8.2](#).

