2.2.3 Pharmacokinetic/Pharmacodynamic Variable(s)

The pharmacokinetic (PK) variables (endpoints) are:

Subset of at least 8 TransCon hGH treated subjects after 13 weeks of treatment:

- PK profile of TransCon hGH over 1 week
- PK profile of hGH over 1 week
- PK profile of PEG over 1 week
- C_{max} for hGH of TransCon hGH

The pharmacodynamic (PD) variables (endpoints) are:

- PD profile of IGF-1 and IGFBP-3 over 1 week
- PD profile of IGF-1 SDS and IGFBP-3 SDS over 1 week

3. Overall Study Design and Plan

This is a phase 3, randomized, open-label, active-controlled trial of TransCon hGH as compared to standard daily growth hormone, over 52 weeks (Figure 1). The trial will be conducted at approximately 100 sites in approximately 20 countries in North America, Europe, Middle East and North Africa, and Oceania. All centers will be specialized treatment centers in the management of pediatric GHD.

The trial consists of:

[figure not shown]
- Screening period - up to 6 weeks (plus approximately 2 weeks between randomization and V1)
- Treatment period - 52 weeks of dosing

The total duration of participation for each subject in the trial will therefore be up to about 60 weeks.

PK/PD profiling and electrocardiogram (ECG) screening bracketing presumed C_{max} of TransCon hGH, hGH, IGF-1, and PEG will be established in a subset of at least 8 TransCon hGH treated subjects (PK/PD subset).

All subjects who successfully complete the 52-week randomized trial will be invited to participate in an extension trial after the treatment period of this 52-week trial has ended. This extension period is to assess long-term safety and efficacy. Subjects on Genotropin treatment (Cohort 2) will be switched over to TransCon hGH treatment for this extension trial.

Figure 1

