All statistical tests except non-inferiority tests will be based on a 2-sided test at the significance level of 0.05 and 95% confidence intervals, unless otherwise specified. Non-inferiority tests will be based on a one-sided significance level of 0.025.

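### SAP 8.3 analyses each child's model-predicted weekly average IGF-1 as if it were observed; because the model is fitted by arm, the nominal p-value and 95% CI of this supportive comparison are anti-conservative

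*SAP*

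**What the plan says.** SAP 8.3 sets out five steps and a second-stage analysis.

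- Step 1: "A non-linear mixed model by treatment will be conducted for IGF-1 concentration data". The data are rich sampling from the Phase 2 paediatric trial, rich sampling from this trial's PK/PD subset, and, for everyone else, "from all sampling data at steady state (visits 3-6) from the rest of the subjects in this study". SAP 3 establishes the rich profiling "in a subset of at least 8 TransCon hGH treated subjects", so it exists in one arm only.
- Step 3: the weekly AUC "will be calculated for each individual subject based on the non-linear mixed model established from Step 2". Steps 4 and 5 divide it by 168 hours and convert it to an SDS.
- Second stage: "The average IGF-1 SDS at Week 52 will be analyzed by an analysis of covariance (ANCOVA) model", and "The proportion of subjects achieving average IGF-1 SDS within 0-2.0 will be analyzed with the same logistic regression model" as in SAP 8.2.

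The opening text of SAP 8 sets the default: "All statistical tests except non-inferiority tests will be based on a 2-sided test at the significance level of 0.05 and 95% confidence intervals". No step in 8.3 reports shrinkage, carries prediction or parameter error forward, or estimates the treatment effect inside the mixed model.

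SAP 8.6 confines formal testing to height velocity: non-inferiority, then superiority. SAP 8.3 describes itself as support for an IGF-1 superiority analysis in 8.2, but states no hypothesis of its own.

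The table list in SAP 13.2 describes something different. Tables 14.2.3.11 and 14.2.3.12 use the mixed model for TransCon hGH only, a plain average for Genotropin, and Weeks 13, 26 and 39 rather than Week 52.

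**The concern.** A child with about four steady-state samples does not determine an individual weekly curve. The mixed model supplies the missing information by pulling the child's prediction toward a fitted mean. With a fit by treatment, that mean is the child's own arm mean. Two things follow.

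- The spread of predictions within an arm is smaller than the spread of the children's own averages.
- The difference between the arm means is not pulled in, so it keeps its full sampling error.

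ANCOVA takes its standard error from the reduced spread and applies it to the unreduced difference. The interval is too narrow and the test rejects a true null too often. The same holds if fitting by treatment means one model with a treatment term, because the predictions are still shrunk to arm-specific means.

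At stake is the analysis that the SAP adds because weekly and daily dosing give different PD profiles, and so the one a reader may trust most for IGF-1. If its p-value and CI are too favourable, the support is overstated.

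**Working it through.** **Inputs from the documents.** Arms of about 100 and 50 (SAP 3.2). About four steady-state samples per child, Visits 3 to 6 (SAP 8.3, Step 1). Phase 2 children: 12 + 14 + 14 = 40 on TransCon hGH (ACP-001) and 13 on Genotropin (Protocol 5.3). Two-sided 0.05 (SAP 8).

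**Assumed.** The between-child SD w and within-child SD s are not given, so s/w is varied. A linear random-intercept model stands in for the compartment model.

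**The plan's own figure.** SAP 8.3 states only the nominal 5%. Simulated ANCOVA on plain, unshrunken child means rejects in 4.7% to 5.7% of runs, which reproduces it.

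**Formula.** The reliability of a child's own mean is R = w²/(w² + s²/4). The by-arm prediction is arm mean + R × (child mean − arm mean). The ANCOVA standard error is then R times the true one, so type I error = 2 × [1 − Φ(1.96 × R)]. For s/w = 1, R = 1/(1 + 0.25) = 0.80, 1.96 × 0.80 = 1.568, and type I error = 11.7%.

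**Simulation.** 100 against 50 children, four samples each, one baseline covariate, true null, 4,000 runs per setting. The fourth column adds the 40 and 13 Phase 2 children to the fit, assuming that they share this trial's arm means. The fifth also assumes that age supplies half of the between-child variance in concentration, with s/w measured against the age-free child SD.

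| s/w | R | Formula | Trial children only | With Phase 2 | With Phase 2 and 50% age share |
|---|---|---|---|---|---|
| 0.5 | 0.94 | 6.5% | 6.8% | 6.0% | 5.4% |
| 0.75 | 0.88 | 8.6% | 8.1% | 7.7% | 5.9% |
| 1.0 | 0.80 | 11.7% | 11.8% | 9.5% | 7.2% |
| 1.5 | 0.64 | 21.0% | 22.6% | 18.2% | 11.3% |

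A separately coded repeat gave 5.9%, 7.9%, 9.7% and 18.6% for the fourth column, and 5.7%, 6.5%, 7.3% and 11.6% for the fifth.

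**Cause.** With one model fitted to both arms together, ANCOVA rejection was 4.6% to 6.4% for R from 0.95 to 0.5 (Monte Carlo error about ±1 point). The arm-specific fit is what does the harm.

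**Logistic analysis.** With the by-arm fit, without Phase 2 children, and with an assumed mean SDS of 0.4 and between-child SD of 1, rejection was 5.2%, 7.2%, 9.7% and 16.5% at R = 0.95, 0.9, 0.8 and 0.7.

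**Table-title reading (TransCon shrunk, Genotropin plain; no Phase 2 children).** At 2:1 the standard error is √[(2R² + 1)/3] times the true one. At R = 0.8 this is √(2.28/3) = 0.872, giving 8.8%; at R = 0.9 it gives 6.7%. Logistic rejection at R = 0.9, 0.8 and 0.7 was 6.9%, 16.2% and 32.3%. It rises faster because shrinking one arm only also biases the proportion inside 0 to 2.0.

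**The case against.** **It is not a confirmatory test.** This stands. SAP 8.6 tests only height velocity, and 8.3 states no null. A reader might infer that the trial's type I error is inflated, or that a formal IGF-1 superiority claim rests on this p-value. The documents do not support either. Protocol 13.4 still plans an IGF-1 superiority test after height-velocity superiority, but Protocol 13 makes the final SAP the analysis of record. What remains is that the SAP 8 default attaches a nominal 0.05 level and 95% CI to this comparison.

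**Analyses without this shrinkage are already planned.** This also stands. SAP 8.2 has an MMRM on observed IGF-1 SDS, an observed average over Visits 3 to 5, and logistic regression on observed 0 to 2.0 rates. They limit the harm. They do not correct 8.3, which was added because single time points compare the two dosing profiles poorly.

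**The size is assumed and could be small.** Correct. A reader might take rates of 20% or more as the expected size. That needs a within-child SD of about 1.5 times the between-child SD or more, and a fit without the Phase 2 children; nothing in the documents supports that ratio, and Step 1 includes those children. The model also works on concentration, where age may add between-child spread and weaken shrinkage. In the other direction, the linear stand-in omits error in the estimated weekly curve that all children in an arm share. The second stage ignores that error too.

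**The SAP does not say that predictions are shrunk.** It does not use the term, but an individual AUC from a mixed model with about four samples per child is a prediction of that kind.

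**Conclusion.** The point holds in direction, with moderate and uncertain size. As written, the ANCOVA and logistic p-values and CIs in SAP 8.3 are anti-conservative whenever within-child error is not negligible. With the Phase 2 children in the fit, ANCOVA type I error runs from about 6% at s/w = 0.5 to about 18% at 1.5, so 95% CI coverage runs from about 94% down to about 82%. With an assumed 50% age share, type I error is about 5% to 11%. These figures rest on an assumed s/w, a linear stand-in model, and Phase 2 children who share this trial's arm means.

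The consequence is limited to the evidence drawn from a supportive IGF-1 comparison. The height-velocity non-inferiority and superiority tests are untouched. The SAP plans no shrinkage report, so a reader of the results could not tell which part of the range applies.

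**What to change.** In SAP 8.3, take the interval and p-value from a procedure that carries the modelling error. Either of these would do:

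- **One joint mixed model** containing treatment and the baseline covariates, with the arm contrast in weekly average IGF-1 reported with that model's own standard error. Pooling both arms without a treatment term and then running ANCOVA is not a substitute: it restores the level but also shrinks a real difference.
- **A bootstrap of children** through Steps 1 to 5 and the second-stage model, using the bootstrap CI. Stratify by arm, study and rich-sampling subset. With 8 rich profiles among 100 children, about 4% of unstratified resamples would draw three or fewer. In 1,000 runs without Phase 2 children, a child-level bootstrap of the two-stage procedure gave 5.0% at s/w = 1.0 and 6.1% at 1.5.

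Also report the shrinkage by arm, and state that 8.3 lies outside the 8.6 hierarchy. Reconcile 8.3 with the titles of Tables 14.2.3.11 and 14.2.3.12 on which arms are modelled and which weeks are covered. That comes first, because modelling one arm only would also bias the 0 to 2.0 proportion.

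The cost is SAP wording and computing, which is not trivial if a compartment model is refitted in every resample. No new data are needed. The CI on a supportive analysis becomes somewhat wider.
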